#### **9.5.3.8 Immunogenicity Testing**

Blood samples will be collected in a 5-mL serum separator collection tube for immunogenicity testing (anti-drug antibody [ADA] and possibly neutralizing antibodies) from all patients prior to dosing on Day 1, and Weeks 3, 12 and 24 (or PW1) (all patients) and Weeks 27, 36 and 48 (or PW2) (non-responders who elect to receive open-label TEPEZZA).

Detailed timing of sample collection for immunogenicity evaluations is described in Section 2.1.

Samples will be collected, processed and stored at  $\geq-70^{\circ}\text{C}$  at the site until shipment to the central laboratory (CC1). The central laboratory will store the samples at  $\geq-70^{\circ}\text{C}$  until shipment to the appropriate laboratory for testing. If a patient tests positive for ADA after

confirmatory and reactive titer testing, the sample will be tested for neutralizing antibodies. If the patient tests positive for neutralizing antibodies, the patient may be followed until levels either return to Baseline or the patient's level decreases or remains stable. ADA samples will be collected during any visit triggered by suspected immunologically related AEs.

Instructions for processing, handling, storing and shipping of immunogenicity samples will be detailed in a laboratory manual that will be provided to each site prior to site initiation.

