3.2.3 Pharmacokinetic and Anti-drug Antibody Endpoints

1. The peak and trough concentrations of TEPEZZA.
2. The anti-drug antibody (ADA) incidence and titers.

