10.4 Other Safety Data

Pregnancy test will be performed at each scheduled visit and the data will be included in a by-subject listing.

For best-corrected visual acuity (BCVA), shift tables for study and fellow eye each will be presented providing the count of patients with each type of finding (i.e., Normal, Mild, Moderate Low Vision, Severe Low Vision and Blindness) at each assessment visit by treatment group for each treatment period. BCVA findings are categorized as follow:

- Normal: 20/12 to 20/40
- Mild: worse than 20/40 to 20/70
- Moderate Low Vision: worse than 20/70 to 20/200
- Severe Low Vision: worse than 20/200 to 20/400
- Blindness: worse than 20/400

11. Immunogenicity: Anti-drug Antibody

ADA samples will be collected prior to the infusion at scheduled visits. If the ADA test is positive after confirmatory and reactive titer testing, the sample will then be tested for neutralizing antibodies (NAb).

Overall positive ADA result for a patient will be defined as at least one post Day 1 confirmed positive ADA result. Cumulative negative result will be defined as negative ADA result at all available time points for a patient.

The reported titer (ratio) value is the minimum required dilution (1:2) * the dilution factor used.

Titer (Ratio) – reported value	Titer (Result) – converted value
1:<2	2
1:x	X

For example, x could be 4, 10, 40, 64, and 100.

The incidence and titer of positive ADA results will be summarized by visit and treatment group using descriptive statistics for the safety analysis set in each treatment period.

All ADA and NAb test results will be presented in a by-subject listing for the safety analysis set in each treatment period.

12. Pharmacokinetics

Pharmacokinetic samples will be collected pre-dose and at the end of infusion on scheduled visits, Day 1, Weeks 3 and 12 of the double-masked treatment period (all patients) and at Weeks 24, 27 and 36 (non-responders who elect to receive open-label TEPEZZA); a single sample will also be collected at Week 24 (or premature withdrawal [PW1]) of the double-masked treatment period (proptosis responders and proptosis non-responders who elect not to receive open-label TEPEZZA) and Week 48 of the open-label treatment period (non-responders who elect to receive open-label TEPEZZA).

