A patient listing of serum concentration-time data will be presented by visit. Teprotumumab peak and trough (i.e., prior to dose) concentrations will be summarized by visit and ADA status (overall positive vs cumulative negative; only to be performed if more than 2 patients receiving TEPEZZA treatment with a positive ADA observed in the trial) using descriptive statistics. The analyses will be based on the PK analysis set in each treatment period.

Further, the mean and CV% (calculated as 100%*SD/mean) of pre-dose serum concentrations will be provided by visit in the subset of patients who are confirmed ADA positive, NAb positive (if applicable) and ADA negative for each visit. This analysis will be provided for the PK Population.

13. Changes in the Planned Analysis

- To ensure the control of the overall Type I error rate in analyzing multiple efficacy endpoints, the process to test individual efficacy endpoints has been added in the SAP section 5 and section 9, as an addition to the protocol.
- TEPEZZA Baseline is defined in the SAP for analysis relative to baseline in the open-label treatment period.
- TEPEZZA study day is defined in the SAP for analysis relative to first dose date during the open-label treatment period.

- To better characterize GO-QoL, analyses of patients with minimal clinically important change in the GO-QoL subscales will be provided.
- Summary and shift tables for chemistry (excluding glucose) will be based on all records (fasting and non-fasting records).

14. References

Heitjan DF and Little RJA. Multiple Imputation for the Fatal Accident Reporting System. *Journal of the Royal Statistical Society, Series C*. 1991; 40:13–29.

Rubin DB. *Multiple Imputation for Nonresponse in Surveys*. New York: John Wiley & Sons. 1987.

Schenker N and Taylor JMG. Partially parametric techniques for multiple imputation. *Computational Statistics & Data Analysis*. 1996; 22:425-446.

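### SAP ADA classes use Day 1 for the negative label but not the positive one, so pre-dose reactivity counts as positive and Day 1-only positives have no class in the PK split

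*SAP*

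**What the plan says.** Protocol Section 9.5.3.8 schedules ADA sampling "prior to dosing on Day 1, and Weeks 3, 12 and 24 (or PW1) (all patients"), with further samples at Weeks 27, 36 and 48 in the open-label period. A pre-dose sample is therefore planned for every patient.

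SAP Section 11 sets two patient-level classes:

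- *Overall positive*: "Overall positive ADA result for a patient will be defined as at least one post Day 1 confirmed positive ADA result".
- *Cumulative negative*: "Cumulative negative result will be defined as negative ADA result at all available time points for a patient".

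The endpoint in SAP Section 3.2.3 is "The anti-drug antibody (ADA) incidence and titers", with no reference to Baseline. Its planned summary in SAP Section 11 reads: "The incidence and titer of positive ADA results will be summarized by visit and treatment group using descriptive statistics". Section 11 also promises a listing: "All ADA and NAb test results will be presented in a by-subject listing".

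The two classes are used in SAP Section 12, which splits peak and trough concentrations as follows: "overall positive vs cumulative negative; only to be performed if more than 2 patients receiving TEPEZZA treatment with a positive ADA observed in the trial". A second Section 12 table gives pre-dose concentrations "in the subset of patients who are confirmed ADA positive, NAb positive (if applicable) and ADA negative for each visit".

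Neither document defines treatment-induced, treatment-boosted or otherwise baseline-adjusted ADA.

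**The concern.** The two definitions rest on different time bases. The positive rule looks only after Day 1, while the negative rule looks at all samples, Day 1 included. Reactivity that was present before any drug can therefore be labelled positive, and one result pattern is left without a label.

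The ADA objective (SAP Section 2.3) is the immunogenicity of TEPEZZA, and pre-dose reactivity is not a response to TEPEZZA. Elsewhere the plan does make this separation. SAP Section 10.1 defines treatment-emergent adverse events from the first dose, and Protocol Section 9.5.3.8 uses Baseline as a reference level when following neutralizing antibodies.

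At stake is the reading of the PK split by ADA status. If some patients in the positive group merely carry pre-existing reactivity, the comparison no longer isolates the effect of drug-induced antibodies on exposure. The by-visit incidence table is affected to a lesser degree, because at later visits it does not distinguish persistent pre-existing positives from new ones.

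**Working it through.** The documents state no ADA rate, so there is no figure of the plan's own to reproduce. The check applies the two definitions to every possible result pattern and then sizes the issue under assumed rates.

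**1. Result patterns.** Each sample is positive or negative. With Day 1 plus k later samples there are 2^(k+1) patterns.

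- Overall positive: at least one later positive, with either Day 1 result, so 2 × (2^k − 1).
- Of these, already positive on Day 1: 2^k − 1.
- Cumulative negative: 1 (all negative).
- Neither class: 1 (Day 1 positive, all later negative).

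| Samples | Patterns | Overall positive | Of which Day 1 positive | Cumulative negative | Neither |
|---|---|---|---|---|---|
| Double-masked, k = 3 (Weeks 3, 12, 24) | 16 | 14 | 7 | 1 | 1 |
| With open-label, k = 6 (adding Weeks 27, 36, 48) | 128 | 126 | 63 | 1 | 1 |

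These are counts of patterns, not frequencies, because the patterns are not equally likely. They show that the positive class does not depend on Day 1 status and that exactly one pattern is unclassified.

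**2. Placebo patients who enter open-label treatment.** Their Day 1, Week 3, Week 12 and Week 24 samples all precede the first TEPEZZA dose; Protocol Section 9.5.6.2.5 requires the Week 24 sample before dosing. Patterns with a positive among Weeks 3, 12 and 24 but none at Weeks 27, 36 and 48 number 2 × (2^3 − 1) = 14 of the 126 overall-positive patterns. In each, every positive result predates TEPEZZA. SAP Section 5.3.5 admits these patients to the PK set once they have a TEPEZZA dose and a post-dose sample. SAP Section 5.4.2 defines a TEPEZZA Baseline for open-label analyses, but Section 11 remains tied to Day 1.

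**3. Size under assumed pre-existing rates p.** With n = 38 TEPEZZA patients (SAP Section 5.1), the expected number of Day 1 positives is 38p, and the chance of at least one is 1 − (1 − p)^38.

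| Assumed p | Expected Day 1 positives | Chance of at least one |
|---|---|---|
| 1% | 0.4 | 0.32 |
| 2% | 0.8 | 0.54 |
| 5% | 1.9 | 0.86 |
| 10% | 3.8 | 0.98 |

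**4. Leverage in the PK split.** The split runs once more than 2 TEPEZZA-treated patients are positive, so at the minimum of three, one pre-existing positive is 1/3 of the group. The text does not say whether a Day 1-only positive counts towards that minimum.

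**The case against.** The strongest reply is that little is lost.

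- A reader might infer that the Day 1 sample is never used. It is: the negative rule covers all time points, and Day 1 is a scheduled ADA visit within the by-visit summary and the listing.
- A reader might infer that Day 1-only positives vanish from the ADA summary. They do not. That summary counts results by visit on the safety set and does not use the two classes, so such a patient appears as positive at Day 1 and negative afterwards.
- Nothing says that the incidence endpoint is the proportion *overall positive*. The documents tie those labels only to the first PK split.
- The second PK table reads as visit-level, so a Day 1-only positive has a place there.
- The placebo arm stands beside TEPEZZA as a guide to background reactivity, and all of this is descriptive.
- Neither document promises a treatment-emergent ADA definition, so there is no internal contradiction.

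All of this stands, and it confines the point. It does not remove three things: the class overlooks Day 1 status and titer rise, one pattern has no place in the two-level PK split, and the by-visit ADA summary cannot separate persistent from new positives. The listing allows reclassification later, but a rule chosen after unmasking would be post hoc.

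**Conclusion.** The point holds as a limited defect in a stated classification rule. Both consequences for Day 1 positives follow from the wording alone. The open-label consequence also assumes that Section 11 applies as written, without a silent switch to TEPEZZA Baseline.

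The impact is descriptive and probably small, and no efficacy analysis is touched. The 0.8 to 3.8 patients rest on an assumed rate of 2% to 10%. A reader might take that range as the number misclassified, but it is an upper bound: a Day 1 positive whose titer later rises enough is rightly called positive. Nor should the same rate be applied to the 19 placebo patients for the double-masked PK comparison, because the SAP's PK set requires a dose of TEPEZZA.

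The change is worth making because it is cheap and the positive group in the PK split may be as small as three.

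**What to change.** In SAP Section 11:

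1. Add a treatment-emergent class: negative at Baseline and confirmed positive later, or positive at Baseline with a later titer rise above a stated threshold. Fix the threshold before unmasking, from assay performance.
2. Assign all other Baseline positives, Day 1-only positives included, to a class for pre-existing, not treatment-emergent ADA. Report that class separately.
3. For the open-label period, use TEPEZZA Baseline (SAP Section 5.4.2) as the reference.
4. Use these classes in the incidence summary and in the SAP Section 12 PK split, and say which class counts towards the more-than-2 condition.

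All 16 double-masked patterns then have a class: 7 treatment-emergent from a negative Baseline, 1 negative, 7 Baseline-positive patterns decided by titer, and 1 Day 1-only pattern in the pre-existing class (7 + 1 + 7 + 1 = 16). At present 15 of 16 are classified.

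The cost is a few lines of SAP text and the work of justifying a titer threshold, which the documents do not give. The samples and titers are already planned. The downside is a slightly smaller ADA-positive group, so the PK split may be less likely to reach its minimum.

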15.1 Schedule of Assessments

Trial Visit	Screening ²	Double-masked Treatment Period									Open-label Treatment Period (Proptosis Non-responders who Choose to Receive Open-label TEPEZZA)									30 days ¹ after W24 or W48/ EOS/ PW
		1	2	3	4	5	6	7	8	9/EOT1/ PW1 ³	10	11	12	13	14	15	16	17/EOT2 / PW2 ³		
Week (W)	-28 days	Day 1/ BL	W3	W6	W9	W12	W15	W18	W21	W24	W27	W30	W33	W36	W39	W42	W45	W48		
Visit Window (±days)			±3	±3	±3	±3	±3	±3	±3	±7	±3	±3	±3	±3	±3	±3	±3	±7	±7	
Informed consent	X																			
Review inclusion/exclusion criteria	X	X																		
Demographics	X																			
Medical history and prior medications ⁴	X ⁵	X																		
Weight ⁶	X				X						X			X				X		
Randomization ⁷		X																		
Efficacy assessments																				
Clinical Measures of Severity – includes proptosis and CCI [REDACTED]	X	X ⁸	X	X	X	X	X		X ⁹	X	X	X	X	X	X	X	X	X		
CCI [REDACTED]		X	X	X	X	X	X		X	X	X	X	X	X	X	X	X	X		
CCI [REDACTED]	X									X								X		
Clinical Activity Score ¹¹	X	X				X				X				X				X		
GO-QoL Questionnaire		X		X	X					X		X	X	X				X		
Treatment response assessment ⁹										X										
Safety assessments																				
Pregnancy test ¹²	X	X	X	X	X	X	X	X	X	X	X	X	X	X	X	X	X	X		

Trial Visit	Screening ²	Double-masked Treatment Period									Open-label Treatment Period (Proptosis Non-responders who Choose to Receive Open-label TEPEZZA)								30 days ¹ after W24 or W48/ EOS/ PW
		1	2	3	4	5	6	7	8	9/EOT1/ PW1 ³	10	11	12	13	14	15	16	17/EOT2/ PW2 ³	
Week (W)	-28 days	Day 1/ BL	W3	W6	W9	W12	W15	W18	W21	W24	W27	W30	W33	W36	W39	W42	W45	W48	
Visit Window (±days)			±3	±3	±3	±3	±3	±3	±3	±7	±3	±3	±3	±3	±3	±3	±3	±7	±7
Visual acuity		X ¹³	X		X	X		X		X		X		X		X		X	
Vital signs ¹⁴		X	X ¹⁴	X ¹⁴	X	X	X	X	X	X ¹⁴	X ¹⁴	X	X	X	X	X	X	X	
Clinical laboratory tests																			
Fasting chemistry		X	X		X	X		X		X		X		X		X		X	
Thyroid function (FT ₃ , FT ₄ , TSH) ¹⁵		X	X			X					X				X			X	
Hematology		X	X		X	X		X		X		X		X		X		X	
HbA1c		X ¹⁶	X			X				X				X				X	
ADA/NAb samples ¹⁷			X	X		X				X	X			X				X	
AE, SAE assessment		X	X	X	X	X	X	X	X	X	X	X	X	X	X	X	X	X	X
Prior/concomitant medications		X	X	X	X	X	X	X	X	X	X	X	X	X	X	X	X	X	X
Pharmacokinetic samples ¹⁸			X	X		X				X	X			X				X	
Biomarker samples ¹⁹			X	X		X				X ²⁰									
Photographs ²¹			X							X								X	
Trial drug infusion			X	X	X	X	X	X	X	X ²²	X	X	X	X	X	X	X		
Contact (phone/email) for safety 24 hours post dose ²³			X ²³	X ²³						X ²³	X ²³								

ADA=anti-drug antibody; AE=adverse event; BL=Baseline; EOS=End-of-Study/Trial; EOT=End-of-Treatment; FT₃=free triiodothyronine; FT₄=free thyroxine; GO-QoL=Graves' Ophthalmopathy Quality of Life; HbA1c=glycated hemoglobin; NAb=neutralizing antibody; PW=premature withdrawal; q3W=once every 3 weeks; SAE=serious adverse event; TSH=thyroid-stimulating hormone; W=week.

Footnotes:

1. All patients will be contacted via phone or email 30 days (±7 days) following the Week 24 (responders and non-responders who choose not to receive open-label TEPEZZA) or Week 48 (non-responders who receive open-label TEPEZZA) Visit.
2. Screening procedures can occur over more than 1 day/clinic visit provided consent is obtained first and all assessments are completed within the designated window.
3. If a patient prematurely discontinues trial drug during the double-masked Treatment Period or the open-label Treatment Period, he/she will return for a clinic visit and undergo the W24/PW1 or W48/PW2 assessments, respectively, with the exception of the collection of blood samples for biomarker evaluations.

4. Medical history will include tobacco, alcohol and other substance use history and thyroid disease history and treatment.
5. Thyroid eye disease must be stable, chronic (inactive) (not progressing, non-sight-threatening but with an appreciable impact on daily life), with thyroid eye disease diagnosed ≥ 3 years but <8 years prior to Screening.
6. The weight obtained at Screening will be used to calculate dose for Day 1 and Weeks 3, 6 and 9. The weight obtained at Week 9 will be used in dose calculations at Weeks 12, 15, 18 and 21. The dose on Weeks 24, 27, 30 and 33 of the open-label Treatment Period will be based on the Week 24 weight; weight measured at Week 33 will be used in dose calculations at Weeks 36, 39, 42 and 45.
7. On Day 1, patients will be randomized in a 2:1 ratio to receive either: a) TEPEZZA (10 mg/kg on Day 1 followed by 20 mg/kg q3W for the remaining 7 infusions) or b) placebo (q3W for all 8 infusions); baseline assessments will be performed prior to dosing.
8. Patients who have a ≥ 2 -mm decrease from Screening in proptosis in the study eye are not eligible for randomization.
9. Response assessment will include whether the patient is a proptosis responder or non-responder; therefore, the proptosis measurement should be one of the first assessments completed during the Week 24 Visit.
10. CCI
[REDACTED]
11. Clinical Activity Score must be ≤ 1 in both eyes at the Screening and Baseline Visits.
12. For women of childbearing potential (including those with an onset of menopause <2 years prior to Screening, non-therapy-induced amenorrhea for <12 months prior to Screening, or not surgically sterile [absence of ovaries and/or uterus]), a serum pregnancy test will be performed at Screening and urine pregnancy tests will be performed prior to dosing at all other visits, as applicable, and at the End-of-Treatment Visit.
13. Patients who have decreased best-corrected visual acuity due to optic neuropathy (defined by a decrease in vision of 2 lines on the Snellen chart, new visual field defect, or color defect secondary to optic nerve involvement within the last 6 months) are not eligible for randomization.
14. Vital signs (blood pressure, heart rate, respiratory rate, temperature) will be measured at all clinic visits. Vital signs will be measured pre- and post-infusion on Day 1 and Week 3 (all patients), pre- and post-infusion at Week 24 and Week 27 (proptosis non-responders who elect to receive open-label TEPEZZA) and pre-infusion on all other infusion days. Additional vital signs will be monitored if infusion-associated AEs occur.
15. Patients must be euthyroid, with the Baseline disease under control or have mild hypo- or hyperthyroidism (defined as FT₄ and FT₃ levels $<50\%$ above or below the normal limits). Every effort should be made to correct the mild hypo- or hyperthyroidism promptly and to maintain the euthyroid state for the full duration of the trial.
16. HbA1c must be $\leq 8.0\%$ to be eligible for the trial. If the HbA1c is elevated and considered clinically significant at any time point after Screening, it will be repeated approximately every 90 days until it returns to normal or Baseline value.
17. ADA sample will be collected prior to the infusion. If the ADA test is positive after confirmatory and reactive titer testing, the sample will then be tested for NAb. If the patient tests positive for NAb, the patient may be followed until levels either return to Baseline or the patient's level decreases or remains stable. ADA samples will be collected during any visit triggered by suspected immunologically related AEs.
18. Pharmacokinetic samples will be collected prior to, and at the end of, the infusion on Day 1, Week 3 and Week 12 of the double-masked Treatment Period (all patients) and Week 24, Week 27 and Week 36 of the open-label Treatment Period (proptosis non-responders who elect to receive open-label TEPEZZA); a single sample will be collected at Week 24 (proptosis responders and proptosis non-responders who elect not to receive open-label TEPEZZA) and Week 48 (proptosis non-responders who elect to receive open-label TEPEZZA).

19. CCI

20. Not collected for patients who prematurely discontinue from the double-masked Treatment Period.
21. For those patients who have consented, photographs of the patient's eyes will be taken prior to the first infusion and at Week 24 (all patients) and Week 48 (non-responders who elect to receive open-label TEPEZZA).
22. For non-responders who choose to receive open-label treatment, TEPEZZA infusion will be performed at Week 24 (first of 8 infusions). All Week 24 assessments except AE and concomitant medication monitoring, post-infusion PK sample collection and 24-hour post-dose phone/email contact must be completed prior to TEPEZZA infusion.
23. Phone (or email) contact by research staff focusing on safety and tolerability aspects will be made the day after infusion for the first and second infusions during the double-masked Treatment Period and during the open-label Treatment Period, and thereafter as deemed appropriate. In addition, patients who experience an infusion-associated event after any subsequent infusion will also be contacted by phone (or email) by research staff the day after the infusion, and thereafter as deemed appropriate.

15.2 Unit Conversion

Quantity	From SI to Conventional Unit	From Conventional Unit to SI
Height	$0.394 \times [\text{cm}] = [\text{in}]$	$2.540 \times [\text{in}] = [\text{cm}]$
Weight	$2.205 \times [\text{kg}] = [\text{lb}]$	$0.454 \times [\text{lb}] = [\text{kg}]$
Temperature	$([\text{°C}] \times 9/5) + 32 = [\text{°F}]$	$([\text{°F}] - 32) 5/9 = [\text{°C}]$

15.3 Graves' Ophthalmopathy Quality of Life Questionnaire

Directions:

- The following questions deal specifically with your thyroid eye disease. **Please focus on the past week while answering these questions.**
- Please tick only one box that matches your answer. The boxes correspond with the answers above them.

15.4 CCI

Research Site Personnel Instructions:

[figure not shown]
Use a ruler to measure the distance, in mm, from the origin (0) to the patient's mark. That distance will be the patient's measure of pain intensity.

Distance measured left Eye: _____ mm
Distance measured right Eye: _____ mm

[figure not shown]
